Protocol

Disseminating Public Health Evidence to Support Prevention and Control of Diabetes Among Local Health Departments

NCT03211832

Updated October 11, 2021

A Stepped Wedge Cluster Randomized Controlled Trial

We will conduct a stepped wedge cluster randomized controlled trial of 12 local health departments (LHDs) in Missouri to evaluate the effectiveness of active D&I approaches on perceived individual and organizational capacity for evidence-based decision making in prevention of diabetes and other chronic diseases.

LHDs will be randomly assigned to three groups that crossover to receive the intervention with measurements at 8-month intervals. No LHDs receive the intervention at baseline. All participating 12 LHDs will receive the intervention, however, for varying durations; group 1 crosses over from control, i.e., usual practice to receive the intervention activities first and for a total of 24 months, group 2 crosses over second and receives the intervention for 16 months, and group 3 crosses over last and receives the intervention activities for 8 months. The intervention activities include a flexible "menu" of D&I approaches that account for local contextual and organizational factors. Dissemination strategies are designed to build workforce and organizational capacity, and may include training in evidence-based public health, technical assistance through a knowledge broker, providing targeted messages/emails with a short summary of the research and actions that might be taken based on the evidence, and organizational changes to assist agency leadership in prioritizing, incentivizing and incorporating the use of EBPPs. LHD practitioners can choose intervention activities from this "menu". This "menu" approach avoids the pitfalls of a "one-size-fits-all" process that is unlikely to be effective across the 12 participating LHDs. Therefore, this study will not attempt to evaluate a single D&I intervention activity but will pursue active, multi-modal approaches, since these are supported in the literature.

Local Health Department Enrollment

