Each LHD will have a designee (most likely the lead chronic disease staff person) who will provide the project coordinator a contact list of staff and practitioners working in and supporting chronic disease control, agency leadership, and staff at key partner agencies. The project/study coordinator will send an email to the list of contacts at the measurement time points (baseline, and three 8-month intervals) inviting them to participate in the dissemination survey. For the network analysis instrument, the invitation will occur at baseline and the last measurement time point.

Table. Stepped wedge group randomized study design.

Shaded cells represent intervention periods (24 months, 16 months, or 8 months).

| | Months | | | |
|-----------------------------|--------|------------------|------------------|-----------------|
| | 1-2 | 3-10 | 11-18 | 19-26 |
| Group 1 (4 LHDs) | | 24 months | | |
| Group 2 (4 LHDs) | | | 16 months | |
| Group 3 (4 LHDs) | | | | 8 months |

For the web-based/online surveys (dissemination survey and network analysis instrument), the first page will be a cover letter containing all elements of consent. The cover letter will include a portion where individuals will be able to choose the statement that best describes how the individual would like to proceed ("Yes, I would like to take the survey," or "No, I prefer not to take the survey."). If a person clicks "Yes, I would like to take the survey," this will indicate her/his consent and s/he will be directed to the start of the survey. If a person clicks "No, I prefer not to take the survey," this will indicate s/he does not consent and s/he will be directed to the end of the survey and no follow up invite/reminders will occur. Project staff will conduct follow up through email and telephone contact. In all contact with potential participants, project staff will emphasize that participation is voluntary. Specifically, health department personnel will be informed that if they choose to take part, they can change their mind and leave the survey. Further, they will be informed that any refusal to participate or withdrawal will not involve a penalty or loss of benefits to which they are otherwise entitled.

Intervention: Individual and Organizational Capacity Building Activities

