The capacity building (intervention) activities seek to build workforce and organizational capacity, and to effectively package and provide information so that it is timely, relevant, and useful for various local-level practitioners. There will be a menu of capacity building (intervention) activities in which each LHD can choose depending on what the LHDs deems important, relevant and feasible. The intervention period for groups begins with workshops as described below. A full set of examples of capacity building activities is shown in an attached table (Intervention Activities). A narrative summary of potential activities are listed below.

1. Targeted dissemination workshops – promoting the use of EBPPs will be modeled after successful workshops that have been conducted to promote evidence-based decision making (Brownson et al., 2009, Gibbert et al., 2013). The workshops will seek to enhance participants' abilities to: understand the role of EBPPs in addressing the diabetes burden; identify diabetes control strategies recommended by evidence-based reviews (e.g., the Community Guide); adapt EBPPs to address health disparities; address organizational barriers to EBPPs; and take action steps to move toward implementation and evaluation of EBPPs. All workshops incorporate principles of science-based training, including: an informal setting, team training, experiential learning, and small group activities applicable to real world experiences. A sample workshop agenda with a brief description of the modules is attached to this IRB form (EBPH Workshop Agenda).

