2. Knowledge brokers – provide a link between research and practitioners by developing a mutual understanding of goals and cultures, collaborating with end users to identify problems for which solutions are required, and enhancing access and use of research evidence in practice and policy. This dissemination strategy has been used more in Canada than in the US. Although the public health literature is sparse with evaluations of knowledge broker impact, there is considerable evidence of effectiveness in other fields, particularly from business and agricultural sectors (Hargadon 2005, Verona et al., 2006, Zook 2004). The knowledge broker activities include: assistance with needs assessments and strategic planning that incorporate EBPPs; consultation on overcoming barriers to EBPPs; help with grant writing that incorporates information from evidence-based sources; and participation in the dissemination workshops described below. Interaction with the brokers will be one-on-one (broker to individuals and teams within the LHD) and it includes face-to-face contact, and remote telephone, email, and video communication.

3. Organizational changes – during the intervention period for each LHD, the research team will work with the LHDs to identify and implement a range of strategies to foster organizational change consistent with Institutional Theory that is part of the project's conceptual framework. Examples of strategies that will be employed will seek to: identify ways agency leadership can prioritize use of EBPPs, develop incentives for use of EBPPs, and incorporate EBPPs as a core component of agency practices (e.g., performance reviews, contracts with local partners).

Data Collection

To evaluate the impact of these intervention activities, we will:

- 1) ask staff/practitioners working in/supporting chronic disease control at each LHD, and their partner organizations to complete the online dissemination survey at four time points (baseline and three 8-month intervals);
- 2) ask for LHD records - program plans and progress reports that LHDs submits to funders, such as the Missouri Department of Health and Senior Services at two time points (baseline and the last data time point);

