- 3) ask for information on the external partnerships of each LHD (baseline and the last data time point), and then ask LHD leadership - manager level and above to complete the online network analysis survey at two time points (baseline and the last data time point). The surveys will be designed for minimal time burden (about 20 minutes).

Power Analysis

This study uses a stepped wedge cluster randomized design. Based on our preliminary studies and values of ICC in the literature, we estimated a range of effect sizes and ICCs. ICC estimates are the most difficult to obtain. We calculated a median ICC from similar studies and developed a range based on a 50% decrease and increase around the median (range 0.009 to 0.027). The sample size requirement is based on testing hypotheses with a power of >90% and the overall Type I error of 5% given 12 clusters (LHDs). The null hypotheses suggest there would be no change in the scores from baseline of three outcomes—awareness, adoption, and maintenance—in all three groups of LHDs (no change). Drawing from our previous work, we hypothesize that the scores will be 17%, 20%, 14% higher for awareness, adoption, and maintenance from baseline to end of study, respectively. Following Baio et. al., and using the most conservative estimates of effect sizes and ICCs, we estimate a need for 12 LHDs, 3 steps or groups (of LHDs), and 10 subjects in each LHD (total = 120) to ensure 5 at the last measure/end of study (total = 60).

Analysis Plan

Descriptive statistics for participant and LHD characteristics and main outcomes will be conducted by trial mode. We will calculate gap in each skill for EBDM by subtracting availability from importance Likert rating (possible range of -10 to +10). An overall skill gap will be created by taking the average across all 10 skill items. We summed all 8 possible EBIs to calculate an “EBI score” which had a possible range of 0-8. For organizational culture items, we grouped and averaged Likert items within six main focus areas based on previous work: awareness of culture supportive of EBDM, capacity and expectations for EBDM, resource availability, evaluation capacity, EBDM climate cultivation, and partnerships to support EBDM (20). A confirmatory

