factor analysis using data from all four time points according to standard procedures demonstrated adequate fit and strict measurement invariance of the factor structure used for the national survey in an earlier study phase. We used linear mixed-effect regression models for each outcome with LHD and Participant entered as random intercepts, trial mode (control or intervention) as fixed effect, and time as a categorical fixed effect. Public health degree, years worked in the public health field, job position category and accreditation status were entered as fixed effects. Kenward-Rogers approximations will be used to determine significance of fixed effects, a common approach in fitting restricted maximum likelihood models in order to produce acceptable Type 1 error. Where models violated assumptions of homoscedasticity, robust models will be approximated. Survey data will be cleaned initially in SPSS and then managed and analyzed in R.

Table. Summary of individual and organizational capacity building (intervention) activities

| Domain | Activity | Description |
|----------------------------------|--|--|
| Accreditation | Accreditation preparations | Local health assessment and plan, formalized decision making, documentation of evidence, documentation reviews, site visit, approval |
| Access to scientific information | Targeted messages | Participants will receive an email indicating that a systematic review related to diabetes or chronic disease control is available |
| Workforce development | Evidence-based decision making (EBDM) training (dissemination workshops) | In-state, in-person multi-day training in EBDM skills, 9 modules, as initial study intervention (this is the kick-off activity for the entire study) |
| | Supplemental brief EBDM skill trainings | Provided by study team or state chronic disease unit, in-person or webinar, as part of this study, with 3 states emphasizing evaluation skills |
| | Non-study national trainings | Hosted in-person EBDM-related skill trainings by national organizations and/or encouraged out-of-state training beyond those required by funders |
| | Quality improvement | Quality improvement or performance management trainings, guidance |
| | New employee EBDM orientation | Via archived webinars or course materials, facilitated discussions, meetings |

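### One on/off term is fitted although exposure lasts 8, 16 or 24 months, so a building effect is understated and a waning one overstated against the equal-weight mean of the three effects.

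*Combined protocol and SAP*

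**What the plan says.** The opening design section states: "All participating 12 LHDs will receive the intervention, however, for varying durations". Groups 1, 2 and 3 (four LHDs each) receive 24, 16 and 8 months, as the design table also shows. Surveys are taken at baseline and at three 8-month intervals (Data Collection).

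For each outcome the Analysis Plan fits a linear mixed model with "LHD and Participant entered as random intercepts, trial mode (control or intervention) as fixed effect, and time as a categorical fixed effect", plus covariates. It has no exposure-duration term, no interaction of trial mode with time and no sensitivity analysis on this point, and it does not say that the coefficient assumes an effect constant over exposure. The robust-model fallback concerns unequal variances only.

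The Power Analysis states its hypothesis for the whole study period: "we hypothesize that the scores will be 17%, 20%, 14% higher for awareness, adoption, and maintenance from baseline to end of study, respectively". It names no weighting over durations.

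**The concern.** The intervention section gives reasons to doubt a constant effect, in both directions. On one side, "The intervention period for groups begins with workshops as described below", and workshops could act early and then level off or fade. On the other, the research team will work with LHDs to "identify and implement a range of strategies to foster organizational change" during the intervention period, and that could build.

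At the last wave no LHD is unexposed. The step in group 3, which has just crossed over, is then judged against groups 1 and 2, which are already exposed. Any further change in those groups is partly absorbed into the time effects. The on/off coefficient therefore gives the longest exposure a negative weight. That weight comes from the design and the correlation; it does harm only when the effect varies with exposure.

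At stake is whether the reported coefficient can be read as the average effect of the programme, or as the end-of-study effect. The planned analysis cannot show which shape applies.

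**Working it through.** **The plan's own figures.** The totals (12 x 10 = 120; 12 x 5 = 60) and the ICC range (0.018 less or plus 50% = 0.009 to 0.027) check. The power above 90% cannot be reproduced because no SD or baseline score is given. Nothing below depends on it.

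**Inputs from the documents.** 12 LHDs, 4 per group; 4 waves; crossover after waves 1, 2 and 3; ICC 0.009, 0.018, 0.027; 10 participants per LHD falling to 5, and up to 22 per LHD.

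**Assumed.** Participant share of within-LHD variance 0, 0.3, 0.5 or 0.7; total variance 1, so effects are in SD; the effect shapes; the equal-weight mean as benchmark. That mean is the mix of exposures at the last wave, when four LHDs have each duration. Covariates are left out.

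**Step 1: weights.** Let d8, d16, d24 be the effects at each duration. Generalised least squares with period effects and LHD and participant random intercepts gives

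E(on/off coefficient) = w8·d8 + w16·d16 + w24·d24, with w8 + w16 + w24 = 1.

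| Setting | w8 | w16 | w24 |
|---|---|---|---|
| No correlation at all (limit) | 0.75 | 0.25 | 0 |
| ICC 0.018, 10 per LHD, share 0 | 0.89 | 0.20 | -0.09 |
| ICC 0.018, 10 per LHD, share 0.5 | 1.10 | 0.13 | -0.23 |
| ICC 0.009 to 0.027, 5 to 22 per LHD, share 0 | 0.80 to 1.02 | 0.16 to 0.23 | -0.18 to -0.03 |
| Same, share up to 0.7 (most extreme) | 1.16 | 0.11 | -0.27 |

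**Step 2: bias for any shape.** Because the weights sum to 1,

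E(coefficient) - (d8 + d16 + d24)/3 = -a·(d16 - d8) - b·(d24 - d16),

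with a = 2/3 - w16 - w24 and b = 1/3 - w24. Over the full grid a = 0.46 to 0.83 and b = 0.36 to 0.61 (at share 0: 0.46 to 0.69 and 0.36 to 0.51). Both are positive at every grid point. So the coefficient is too low for any effect that never falls and rises at some step, and too high for any that never rises and falls at some step. The terms cancel only if the second step reverses the first and is a/b = 1.27 to 1.36 times as large.

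**Step 3: one case by hand** (ICC 0.018, 10 per LHD, share 0, rounded weights).
- Building: 0.89 x 0.2 + 0.20 x 0.4 - 0.09 x 0.6 = 0.204, against 0.40.
- Waning: 0.89 x 0.4 + 0.20 x 0.3 - 0.09 x 0.2 = 0.398, against 0.30.

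**Step 4: assumed shapes over the full grid (SD).**

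| Effects at 8/16/24 months | Equal-weight mean | Expected coefficient |
|---|---|---|
| Building 0.2/0.4/0.6 | 0.40 | 0.11 to 0.23 |
| Waning 0.4/0.3/0.2 | 0.30 | 0.38 to 0.44 |
| Early plateau 0.3/0.4/0.4 | 0.37 | 0.28 to 0.32 |
| Rise then fall 0.30/0.40/0.27 | 0.323 | 0.320 to 0.324 |

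**Step 5: robustness.**
- Attrition: with 10, 8, 7 and 5 participants by wave (the middle two assumed), a = 0.48 to 0.76, b = 0.36 to 0.52, building 0.14 to 0.23, waning 0.38 to 0.43.
- Unequal sizes: in 1,500 random sets of unequal LHD sizes with dropout, w24 was below w8 every time. That fixes the sign for a steady linear change, whose bias is (w24 - w8) times the change per 8 months.
- Fitting the model by REML: 1,000 simulated trials at ICC 0.018 and 10 per LHD gave, at shares 0 and 0.5, building 0.189 and 0.125, waning 0.399 and 0.430, and constant 0.30 as 0.298 and 0.296 (Monte Carlo SE 0.005 and 0.004).

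**Step 6: does the alternative work?** With indicators for 8, 16 and 24 months in place of trial mode, the design is estimable (rank 7 of 7) and the equal-weight mean is recovered exactly: 2.000 for both 1, 2, 3 and 3, 2, 1.

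**The case against.** The strongest reply is that the bias is conditional. The documents give no shape, a constant effect produces no bias, and no effect at any duration produces no false positives. That stands, and it is why the main model should stay.

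The equal-weight mean is also a choice. Exposed LHD-waves split 12:8:4 over the three durations, and a 3:2:1 average is equally natural for an on/off term. Against it, the building example has mean (3 x 0.2 + 2 x 0.4 + 0.6)/6 = 0.333 and a shortfall of 0.10 to 0.22, not 0.17 to 0.29. The waning example has mean (3 x 0.4 + 2 x 0.3 + 0.2)/6 = 0.333 and an excess of 0.05 to 0.11, not 0.08 to 0.14. The sizes shrink; the directions do not change. The most extreme figures also need a participant share of 0.7, which is an assumption.

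Nor is the alternative always the more accurate estimator. At 10 per LHD, against the equal-weight mean, the on/off coefficient has the smaller root-mean-square error at all 12 grid points for early plateau, at 4 of 12 for waning and at none for building. This supports reporting both estimates; it does not support leaving the assumption unstated and unexamined.

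**Conclusion.** The concern holds. The coefficient equals the equal-weight mean with certainty only if the effect is constant over exposure; some rise-then-fall patterns match it by coincidence. Otherwise an effect that only builds is understated and one that only wanes is overstated. For the assumed shapes, 0.40 SD becomes 0.11 to 0.23 and 0.30 SD becomes 0.38 to 0.44. For an outcome where benefit is a fall in score, presumably the skill gap, read this as magnitude.

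The direction rests on the stated model and design, and it held at every ICC, cluster size and participant share tried. The sizes rest on the assumed shapes, participant share and benchmark. The distortion in this trial is unknown. This is an improvement that should be made; the planned model is not invalid.

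**What to change.** Keep trial mode as the main analysis and state that it assumes an effect constant over exposure. Describe its coefficient as an average under that assumption, not as the end-of-study effect.

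Add a sensitivity analysis in the same mixed model, with indicators for 8, 16 and 24 months since crossover in place of trial mode. Report the three effects and their equal-weight average with confidence intervals. State two limits:
- It assumes that the effect at a given exposure is the same across calendar waves and groups, although "There will be a menu of capacity building (intervention) activities in which each LHD can choose".
- The 24-month effect rests on group 1 at the last wave, when no LHD is unexposed.

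Report both analyses; do not let a significance test of their difference decide between them. The expected difference is 0.67 to 2.04 of its own standard errors for the waning example and 1.34 to 4.09 for the building one, so such a test could easily miss a real distortion.

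The Analysis Plan describes the models partly in the past tense and reports a factor analysis of all four waves. If the models have already been fitted, label the addition post hoc.

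**Cost.** A paragraph and a few lines of R, with no new data. The statistical price is:
- The average's standard error is 17% to 52% above the on/off one (23% to 50% with attrition). At ICC 0.018 and 10 per LHD it is 0.182 against 0.148 at share 0, and 0.166 against 0.116 at share 0.5.
- The 24-month effect is imprecise: SE 0.21 to 0.29 SD at 10 per LHD, and 0.26 to 0.36 SD if numbers fall to 5.
- If group 3's 8-month effect were 0.1 SD larger than that of the other groups, the averaged estimate would fall by about 0.03 SD while the true last-wave mean rose by 0.03 (0.1/3), an error of about 0.06. The 24-month estimate would fall by 0.06 to 0.07 SD.
- The Analysis Plan's eight scores (skill gap, EBI score, six culture scores) would each gain four estimates, 8 x 4 = 32 in all, so they should be presented as supporting results.

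### Does adjusting for accreditation status, with no measurement time given, take part of the intervention's effect out of the trial-mode coefficient?

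*Combined protocol and SAP*

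**What the plan says.** The Analysis Plan specifies a linear mixed model for each outcome, with "LHD and Participant entered as random intercepts" and "trial mode (control or intervention) as fixed effect, and time as a categorical fixed effect". It then lists the adjustment terms: "Public health degree, years worked in the public health field, job position category and accreditation status were entered as fixed effects". No section defines accreditation status or says when it is recorded.

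The closing table, titled "Summary of individual and organizational capacity building (intervention) activities", has accreditation preparations as its first row, described as "Local health assessment and plan, formalized decision making, documentation of evidence, documentation reviews, site visit, approval". The section on the intervention says "There will be a menu of capacity building (intervention) activities in which each LHD can choose". The opening description of the design states the target: "this study will not attempt to evaluate a single D&I intervention activity but will pursue active, multi-modal approaches".

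Data Collection lists the dissemination survey at four time points, and LHD (local health department) records, partnership information and a network survey at two. It does not mention recording accreditation, once or repeatedly.

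**The concern.** The trial evaluates the package as a whole, so the quantity of interest is its total effect on the scores. A covariate that the package can change lies between intervention and outcome. If the model holds it fixed, the trial-mode coefficient leaves out whatever works through it.

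Accreditation status looks like such a covariate. Preparing for it is on the menu, the description of that activity ends in approval, and exposure lasts 8, 16 or 24 months depending on the group. The link to the outcomes is also plausible: the accreditation row includes formal decision processes and documented evidence, and the culture outcomes include capacity and expectations for evidence-based decision making. With four surveys and no stated timing, one analyst could use the baseline value and another the current one. The second could report too small an effect.

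**Working it through.** **The plan's own figures.** The Power Analysis gives 12 LHDs with 10 subjects each (12 × 10 = 120), to leave 5 each at the end (12 × 5 = 60). It gives no figure for accreditation. It also gives no SD or baseline mean, so the effect in SD units has to be assumed.

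**Inputs from the documents.** 12 LHDs in 3 groups of 4; 4 surveys; 10 subjects per LHD; ICC 0.009 to 0.027.

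**Assumed inputs.** Total effect 0.3 SD; score difference between accredited and unaccredited LHDs (γ) 0.1 to 0.3 SD; participant-level share of variance (p) 0.3 to 0.5; 10 subjects at every survey.

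**Method.** Let δ be the generalised least squares coefficient of trial mode when the accreditation indicator is regressed on trial mode and categorical time. The weights come from the model's own covariance. For LHD-by-survey means with total variance 1, that covariance is (ICC + p/10) between any two surveys, plus (1 − ICC − p)/10 on the diagonal. Then:

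- coefficient without current status = coefficient with current status + γ × δ
- share of the effect lost = γ × δ / 0.3

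If one LHD in each group changes at crossover, the group mean of accreditation is exactly one quarter of trial mode at every survey. So δ = 3/12 = 0.25 whatever the variances. The other values depend on the variances; a recalculation for this note gave the same ranges.

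| LHDs gaining approval | By which survey after crossover | δ | γ × δ (SD) | Share of 0.3 SD |
|---|---|---|---|---|
| None | – | 0 | 0 | 0% |
| One in group 1 | First | 0.097 to 0.122 | 0.010 to 0.037 | 3% to 12% lost |
| One per group | First | 0.25 | 0.025 to 0.075 | 8% to 25% lost |
| One per group (group 3 has no second survey, so its LHD does not change) | Second | −0.003 to −0.028 | up to 0.008 in size | under 3%, upward |
| One in group 1 | Third | −0.044 to −0.060 | 0.004 to 0.018 in size | 1.5% to 6%, upward |

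For example, 0.122 × 0.3 = 0.037 and 0.037 / 0.3 = 12%; 0.028 × 0.3 = 0.008 and 0.008 / 0.3 = 2.8%.

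**Check by simulation.** This used 4,000 trials with ICC 0.018, p = 0.4, γ = 0.3 and true total 0.30. With one group 1 LHD approved by its first survey, the coefficient was 0.299 with baseline status and 0.267 with current status. The difference of 0.032 gives δ = 0.032 / 0.3 = 0.107, inside the range above. With one LHD per group, the values were 0.301 and 0.226, a difference of 0.075 = 0.25 × 0.3.

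**A second set of assumptions.** Here the direct effect was 0.40 SD, γ was 0.2 or 0.4, and each unaccredited LHD gained approval with probability 0.10 to 0.50 in each intervention period. The loss was 0.02 to 0.17 SD, about 4% to 30%. It was zero when no LHD changed. Fitting baseline status gave the same coefficient as leaving the term out, to within 0.002.

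**Size against noise.** The SD of the simulated coefficient was 0.125. The one-LHD loss is 0.010/0.125 to 0.037/0.125, or 0.1 to 0.3 of that; the one-per-group loss is 0.025/0.125 to 0.075/0.125, or 0.2 to 0.6.

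**The case for a change.** The strongest case for a change is that the plan lists work towards a status as an intervention activity and then adjusts for that status, without excluding values recorded after crossover. A sentence fixing it at baseline would cost almost nothing. Precision would not suffer: the SD of the coefficient was 0.125 with baseline status and 0.126 to 0.129 with current status. With fast uptake and a large γ, the loss reaches 25% to 30%, which would matter.

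The two textual facts stand: the timing is unstated, and the activity is on the menu. The step from there to harm is weak.

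- The activity is preparation. The narrative of the intervention covers workshops, knowledge brokers and organizational changes and never names accreditation. It calls the table a set of examples, and another row of that table refers to 3 states although this trial is in Missouri alone. The row is thin evidence of what was delivered.
- The losses tabulated above need plans, documentation, reviews, site visit and approval to be finished within about 8 months of crossover. The one-per-group figure needs this even in group 3, whose whole exposure is 8 months.
- Current status is not plainly inferior. If an LHD gained accreditation for reasons unrelated to the trial, the current value would adjust for a real influence that the baseline value misses. The simulations do not cover that case.
- Fixing degree, years worked and job position at the first survey would add little. For staff who are first surveyed after crossover, that survey is not a baseline.

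**Conclusion.** The concern does not call for a change. The plan leaves one detail unstated. The usual choice for a background characteristic of a cluster is its value at baseline, and with that choice the problem does not arise. Nothing in the documents says that status was updated, that any LHD changed status, or that status affects the scores, and all three are needed for a loss.

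If all three held, the size would depend on timing: 3% to 12% for one early approval in group 1, 8% to 25% for one early approval per group, up to about 30% with rapid and widespread uptake, and a small upward shift for a single later approval. These figures rest on the assumed effect sizes and variance shares, not on values in the documents. The true figure may be zero. No stated rule has been shown to give a wrong result. A reader of the results need only note which value of accreditation status was used.
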